11. DATA MANAGEMENT

11.1. Access to Data

Direct access will be granted to authorised representatives from the University of Oxford and any host institution for monitoring and/or audit of the study to ensure compliance with regulations.

11.2. Data Handling and Record Keeping

All study data will be entered on MACRO, the Clinical Data Management System. The study database will be developed according to the approved Case Report Forms (CRFs). As for documents that contain patient identifiers, only the site PIs will have access to these documents.

The MORU Data Management Standard Operating Procedures will be followed in the study. After the study is closed, the study documents will be kept in the accessible storage on request for 15 years. The final dataset will be archived in the data repository after the publication.

12. QUALITY CONTROL AND QUALITY ASSURANCE PROCEDURES

The study will be conducted in accordance with relevant regulations and standard operating procedures.

12.1 Study monitoring

An appointed study monitor from the MORU clinical trial support group and a project coordinator will regularly visit the study sites for quality control. All study sites will be assessed prior to initiation of the study for capacity to conduct the randomised controlled trial, during the study and upon completion to ensure data quality. After site initiation, monitoring visits will perform monitoring on informed consent forms, CRF for completeness and accuracy of data and sample storage. There will be a minimum of three monitoring visits per study site: after 3-5 participants enrolled, after 50% of the target sample size enrolled for a particular site and upon study completion. Monitoring reports will be made available to the study sites and investigators after each visit.

12.2 Strategies to improve adherence

Regular meetings with the study sites will be carried out to ensure buy-in from the physicians and healthcare providers. Their feedback will be sought throughout the study, and improvements will be made in the study procedures to maintain ongoing support from the local ICUs. The study team will contact the primary physicians prior to enrolment and randomisation to ensure their adherence to allocated interventions.

13. ETHICAL AND REGULATORY CONSIDERATIONS

13.1. Declaration of Helsinki

The CI will ensure that this study is conducted in accordance with the principles of the Declaration of Helsinki.

13.2. Guidelines for Good Clinical Practice

The CI will ensure that this study is conducted in accordance with relevant regulations and with Good Clinical Practice.

13.3. Approvals

The protocol, participant information sheet and informed consent form will be submitted to OxTREC and local ethics committees for written approval.

The Investigator will submit and, where necessary, obtain approval from the above parties for all amendments to the original approved documents.

13.4. Participant Confidentiality

The study staff will ensure that the participants' anonymity is maintained. The participants will be identified only by a participant ID number on all study documents and any electronic database, with the exception of the CRF, where participant initials will be added. All documents will be stored securely and only accessible by study staff and authorised personnel. The study will comply with the Data Protection Act, which requires data to be anonymised as soon as it is practical to do so.

13.5. Expenses and Benefits

The study team will reimburse reasonable travel expenses for any visits additional to normal care.

13.6. Reporting

The CI shall submit an Annual Progress Report to OxTREC and local ethics committees on the anniversary of the date of approval of the study. In addition, the CI shall submit an End of Study Report to OxTREC and local ethics committees.

14. FINANCE AND INSURANCE

14.1. Funding

The project will be partly funded by Medical Research Council/ Department for International Development (MRC/DfID) (Grant Ref: MR/K006924/1) and Singapore National Medical Research Council (Grant Ref: CTGIIT18MAY-005).

14.2. Insurance

Specialist insurance policy is in place, which would operate in the event of any participant suffering harm as a result of their involvement in the research (Newline Underwriting Management Ltd, at Lloyd's of London).

15. PUBLICATION POLICY

The CI will coordinate writing and reviewing of drafts of the manuscripts, abstracts, and any other publications arising from the study. Authorship will be determined in accordance with the ICMJE guidelines and other contributors will be acknowledged.

[figure not shown]

17. APPENDIX A: STUDY FLOW CHART

1. Patients who satisfy all the inclusion criteria below may be recruited:

- a. Patients 18 years and older, and
- b. Invasive mechanical ventilation ≥ 48 hours, and
- c. Satisfy the US Centers for Disease Control and Prevention National Healthcare Safety Network VAP diagnostic criteria [29]
 - o At least one of the following:
 1. temperature > 38 °C
 2. white blood cell count $\geq 12,000$ cells/mm³ or $\leq 4,000$ cells/mm³
 3. altered mental status with no other causes in >70 year-olds; and
 - o Two or more chest imaging tests demonstrating at least one of the following:
 1. new and progressive OR progressive and persistent infiltrate
 2. new and persistent OR progressive and persistent consolidation
 3. new and persistent OR progressive and persistent cavitation, and
 - o At least two of the following:
 1. new onset of purulent sputum, or change in character of sputum, or increased respiratory secretions, or increased in suctioning requirements
 2. new onset or worsening tachypnea or dyspnea
 3. rales or bronchial breath sounds
 4. worsening gas exchange defined by oxygen desaturations (e.g., $\text{PaO}_2/\text{FiO}_2 < 240$), increased oxygen requirements or increased ventilation demand

2. Respiratory cultures can be quantitative or non-quantitative, invasive or non-invasive.
3. For those participants randomised to the intervention (short duration) arm, site investigators should assess the participants daily. Antibiotics should be stopped, if the criteria below are satisfied,
 - a. body temperature was $\leq 38.3^{\circ}\text{C}$ (core body temperature measured orally or rectally) or 38.0°C (axillary) for 48 hours, and
 - b. hemodynamic instability (systolic blood pressure ≥ 90 mm Hg without inotropic support or no requirement of inotropic support to maintain systolic blood pressure above 90 mm Hg).

18. APPENDIX B: SCHEDULE OF STUDY PROCEDURES

Procedures	Visit timing Day 0	Daily during hospitalisation	Weekly during hospitalisation	Day 28/60 (± 5)
	Screening and enrolment			Follow up visit/ Last visit
Informed consent	X			
Demographics	X			
Medical history and medical record review	X	X	X	X
Review antibiotics administration records	X	X	X	X
Physical examination	X			
Eligibility assessment	X			
Randomisation once clinical criteria for stability met		X		
Respiratory microbiology culture	X			
Stool and sputum sample for microbiome study	X		X	X
Review of antibiotics and stop antibiotics if criteria fulfilled		X		
Adverse event assessments (throughout the study)		X	X	X

1. INTRODUCTION

This document details the proposed presentation and analysis for the Reducing antibiotics treatment duration for ventilator-associated pneumonia trial (REGARD-VAP). Any primary reporting of the REGARD-VAP study should follow the strategy set out in this document. Subsequent analyses of a more exploratory nature will not be bound by this strategy, though they are expected to follow the broad principles laid down here. The principles are not intended to curtail exploratory analysis nor to prohibit accepted practices (for example, data transformation prior to analysis), but they are intended to establish the rules that will be followed, as closely as possible, when analysing and reporting the trial.

The analysis strategy will be available on request when the principal papers are submitted for publication in a journal. Suggestions for subsequent analyses by journal editors or referees will be considered carefully, and carried out as far as possible in line with the principles of this analysis strategy; if reported, the source of the suggestion will be acknowledged. Any deviations from the statistical analysis plan will be described and justified in the final report of the trial. The analysis should be carried out by an identified statistician, who should ensure the integrity of the data during their processing. Examples of such procedures include quality control and evaluation procedures.

2. BACKGROUND INFORMATION

2.1. Objectives

Primary objective

To assess the effect of short (7 days or fewer depending on clinical response) versus long (8 days or more depending on physicians' preference) antibiotic treatment strategies on mortality and pneumonia recurrence within 60 days of enrolment in adults with ventilator-associated pneumonia (VAP) in Asia.

Secondary objectives

To compare the following endpoints according to treatment allocation within 60 days of enrolment:

- a) Ventilator-associated events
- b) Duration of mechanical ventilation
- c) Duration of hospitalisation
- d) Acquisition of multidrug resistant infection or colonisation during the hospitalisation
- e) Number of days of exposure to antibiotics during hospitalisation
- f) Number and types of extrapulmonary infections during hospitalisation (determined from cultures taken from sterile sites)
- g) Adverse events, i.e. antibiotic related diarrhoea, allergic reactions, readmissions

2.2. Study Design

The study design is a randomised, partially double-blinded (blinding may be achieved up to 7 days) controlled trial to assess the efficacy of short versus longer antibiotics course in adults with VAP. The trial has a stepwise noninferiority–superiority hypothesis, i.e. if non-inferiority of short duration, compared with long duration, is shown, statistical tests for superiority will be performed using closed testing methods without requiring adjustment of the significance level for multiple comparisons.

Period of external pilot	19 February 2018 to 23 May 2018
Date of start of recruitment	25 May 2018
Date of end of recruitment	16 December 2022
Date of end of follow-up	14 February 2023
Date of expected analysis	14 March 2023 to 14 May 2023
target number of participants	460 (230 per arm)

Participating study sites include:

- 1) National University Hospital, Singapore
- 2) Tan Tock Seng Hospital, Singapore
- 3) Sunpasitthiprasong Hospital, Ubon Ratchathani, Thailand
- 4) Srinagarind Hospital, Khon Kaen, Thailand
- 5) Patan Academy of Health Science, Patan Hospital, Kathmandu, Nepal
- 6) Civil Hospital, Kathmandu, Nepal
- 7) Khon Kaen Hospital, Khon Kaen, Thailand
- 8) Cajuru University Hospital, Pontifical Catholic University of Paraná, Brazil

2.3. Eligibility

Adult patients (≥ 18 years old) in participating wards who have been on mechanical ventilation for more than 48 hours who satisfy the following criteria are eligible for the study.

Inclusion Criteria

- a. Patients 18 years and older

- b. Invasive mechanical ventilation \geq 48 hours
- c. Satisfy the US Centers for Disease Control and Prevention National Healthcare Safety Network VAP diagnostic criteria ¹
 - o At least one of the following:
 1. temperature $> 38^{\circ}\text{C}$
 2. white blood cell count $\geq 12,000 \text{ cells/mm}^3$ or $\leq 4,000 \text{ cells/mm}^3$
 3. altered mental status with no other causes in > 70 year-olds; AND
 - o Two or more chest imaging tests demonstrating at least one of the following:
 1. new and progressive OR progressive and persistent infiltrate
 2. new and persistent OR progressive and persistent consolidation
 3. new and persistent OR progressive and persistent cavitation, AND
 - o At least two of the following:
 1. new onset of purulent sputum, or change in character of sputum, or increased respiratory secretions, or increased in suctioning requirements
 2. new onset or worsening tachypnea or dyspnea
 3. rales or bronchial breath sounds
 4. worsening gas exchange defined by oxygen desaturations (e.g., $\text{PaO}_2/\text{FiO}_2 < 240$), increased oxygen requirements or increased ventilation demand

Exclusion Criteria

- a. Poor likelihood of survival as defined by a Sepsis-related Organ Failure Assessment score (SOFA score) of > 11 points ²

- b. Immunocompromised patients (HIV with CD4 <200 cells/mm³, corticosteroids > 0.5 mg/kg per day for > 30 days, received chemotherapy in the past 3 months, solid organ or hematopoietic cell transplant)
- c. Patients receiving antibiotic therapy for any other defined extra-pulmonary infections that warrant a duration of antibiotics longer than 7 days or complications of pneumonia such as lung abscess or empyema that warrant a duration of antibiotics longer than 7 days (excluding anti-tuberculosis treatment, antifungal medications, antibiotics meant for chronic suppression of chronic infections or chronic obstructive lung disease)
- d. Patients who have been treated for VAP for more than 7 days from screening
- e. Vulnerable population including prisoners and refugees

2.4. Treatment interventions

Randomisation

Randomisation will be done via stratified block randomisation by the study sites to ensure participants with similar characteristics such as sex and age are distributed equally in the intervention and control groups. Randomisation will be done with a computer program with a seed to allow reproducibility. Randomisation will be done with a 1:1 ratio. To prevent predictability of the random sequence, generation of the randomisation sequence is performed by an independent statistician and details of the randomisation generation is unavailable to all investigators. Randomisation will be allocated using sequentially numbered opaque envelopes. Fitness criteria for randomisation must be met prior to randomisation.

Antibiotic choice

Antibiotic treatment for VAP will be tailored to the susceptibility of the pathogen(s) and in accordance to the 2016 IDSA/ATS VAP guideline³. Primary physicians are encouraged to convert initial empirical regimen to narrow- spectrum therapy based on culture results. In culture-negative cases, empirical antibiotic choice should be made depending on local

antibiogram. The study team will not intervene on the antibiotics choices as this is beyond the objectives of the study.

Antibiotic duration

Number of days of antibiotics is calculated from the first day of appropriate coverage according to the susceptibility of at least 1 of the pathogen(s) recovered from respiratory cultures taken within 48h of screening or VAP symptom onset.

For those participants randomised to the intervention (short duration) arm, site investigators should assess the patients daily. Antibiotics should be stopped at

- a) day 3 to 7, if all respiratory cultures during the same episode of VAP are negative, given that the criteria below are satisfied,
- b) day 5 to 7, if any of the respiratory cultures are positive and positivity is attributable to the current episode of VAP, given that the fitness criteria below are satisfied,
 - a. body temperature was $\leq 38.3^{\circ}\text{C}$ (core body temperature measured orally or rectally) or 38.0°C (axillary) for 48 hours, and
 - b. lack of hemodynamic instability (systolic blood pressure ≥ 90 mm Hg without inotropic support or no requirement of inotropic support to maintain systolic blood pressure above 90 mm Hg).

In the short duration arm, all antibiotics should be withdrawn by day 7 (short duration) according to the randomisation assignment, except for those participants with treatment failure in the case of persistent VAP or a new-onset infection of a different source prior to the last day of assigned duration of antibiotics. Persistent VAP or treatment failure is defined as the lack of improvement of hemodynamic stability or ventilation requirements without an alternative cause other than the same episode of VAP. These patients will continue to be monitored for the above-described “fitness criteria” and antibiotics should be stopped when they eventually meet the criteria. Recurrent VAP is defined as an additional episode of VAP satisfying the CDC clinical and radiological criteria of VAP¹ following commencement of the primary VAP treatment within $60(\pm 5)$ days of enrolment. Opinion from 2 respiratory experts blinded to the randomisation will be sought to diagnose persistence and recurrences. Patients who are diagnosed with an alternative source of

infection or a complication from VAP such as lung abscess or empyema that warrant a duration of antibiotics longer than 7 days prior to the last day of assigned duration of antibiotics are not considered treatment failures. These patients will not meet fitness criteria for randomisation and be discontinued from the study and subsequent analysis. In cases where patients are randomised to short duration and satisfy the above-described “stop criteria” but did not have their antibiotics stopped by day 7, they are considered protocol deviations. They will be analysed in the intention to treat analysis according to arm they are randomised to.

Duration of antibiotics in the control group will be at least 8 days with the exact duration decided by the managing physicians.

Adverse events will be recorded throughout the study period, including *C. difficile* infection, acute kidney injury, hepatitis, drug allergies, haematological and other complications, readmissions.

Blinding

Patients will be blinded to the study arm they are randomised to, as they will not be informed of the treatment duration and are likely to be sedated and unaware of the treatment regimens. Investigators will be blinded during the assessment of the participants for clinical stability based on the above-described criteria to minimise observer bias. Once conditions for stopping antibiotics are satisfied, the investigator will be unblinded and contact the primary physicians to stop antibiotics. The physicians will remain blinded until they are informed that the participant is suitable to stop antibiotics. Independent assessors, who are assigned to determine pneumonia recurrences, will be blinded from the randomisation arms. This will be achieved by blinding these independent assessors to study details which could be used to determine the allocation arm, including antibiotic treatment, for participants with potential recurrences from.

2.5. Non-inferiority margin and sample size

The study is designed as a hierarchical non-inferiority /superiority trial where, if non-inferiority can be established, superiority will be assessed. The primary outcome is the composite endpoint of mortality and recurrence at 60(± 5) days of the short duration versus

the long duration of antibiotic treatment for VAP. A meta-analysis showed that mortality attributable to VAP ranges from 13.6 to 42.8% in Southeast Asia⁴. Considering that our primary outcome is a composite binary outcome of mortality and recurrence of VAP, we estimate this to be 55%. We derived an absolute non-inferiority margin of 12% with the fixed-margin method, preserving at least 50% of the efficacy of standard treatment in VAP. Using a group sequential design adopting the boundaries proposed by Fleming- Harrington- O'Brien ($R=0.8$)⁵, a maximum of 412 patients will be required to achieve a power of 80% to conclude non-inferiority between the two groups with an one-sided α risk of 5%. As we anticipate a loss to follow-up of up to 10%, we plan to enrol a maximum of 460 patients.

2.6. Hypotheses and Definition of Primary and Secondary Outcomes

Primary end point

The primary end point of the study is the difference in the proportion of participants with the composite endpoint of death and VAP recurrence rate within 60(± 5) days of enrolment.

Death refers to all-cause mortality. VAP recurrences are episodes which satisfy the US CDC VAP criteria, and verified by two independent respiratory or infectious diseases physicians blinded to the randomisation arm.

The first statistical test for the primary end point will be for non-inferiority. Here, the null hypothesis (H_0): $\theta \geq \delta$ will be tested against the alternative (H_1): $\theta < \delta$, where θ is the treatment effect difference between the proportion of participants who have the primary outcome in the short and long treatment strategy groups, and δ is the fixed non-inferiority margin of 12%.

In the event that short is non-inferior to the long treatment strategy, standard two-sided superiority testing will be performed. That is, the null hypothesis (H_0): $\theta = 0$ will be tested against the alternative (H_1): $\theta > 0$, where θ is the treatment effect difference between the proportion of participants who have the primary outcome in the short and long treatment strategy groups.

Secondary end points

All statistical tests for the secondary endpoints are standard two-sided superiority tests.

a) Ventilator-associated events

Definition: Events which satisfy the US CDC VAP criteria ¹ but were not verified by two independent respiratory or infectious diseases physicians.

H_0 : There is no difference in the proportion of participants who have ventilator-associated events in the short and long treatment strategy groups, i.e. $\theta^{VAE} = 0$;

H_1 : There is a difference in the proportion of participants who have ventilator-associated events in the short and long treatment strategy groups, i.e. $\theta^{VAE} \neq 0$;

where θ^{VAE} is the treatment effect difference between the proportion of participants in the short and long treatment strategy groups.

b) Duration of mechanical ventilation

Definition: Total duration of mechanical ventilation during the 60 days of follow-up after enrolment.

H_0 : There is no difference in the total duration of mechanical ventilation in the short and long treatment strategy groups, i.e. $t^v_s = t^v_l$;

H_1 : There is a difference in the total duration of mechanical ventilation in the short and long treatment strategy groups, i.e. $t^v_s \neq t^v_l$;

where t^v_s is the duration of mechanical ventilation in the short and t^v_l is the duration of mechanical ventilation in the long treatment strategy groups.

c) Duration of hospitalisation

Definition: Total duration of hospitalisation during the 60 days of follow-up after enrolment.

H_0 : There is no difference in the total duration of hospitalisation in the short and long treatment strategy groups, i.e. $t^h_s = t^h_l$;

H_1 : There is a difference in the total duration of hospitalisation in the short and long treatment strategy groups, i.e. $t^h_s \neq t^h_l$;

where t^h_s is the duration of mechanical ventilation in the short strategy group and t^h_l is the duration of mechanical ventilation in the long treatment strategy group.

d) Acquisition of multidrug resistant infection or colonisation during the hospitalisation

Definition: Growth of multidrug resistant bacteria⁶ from clinically indicated or screening cultures from any source during 60 days of follow-up.

H_0 : There is no difference in the proportion of participants who colonised with multidrug resistant bacteria in the short and long treatment strategy groups, i.e. $\theta^{\text{MDR}} = 0$;

H_1 : There is a difference in the proportion of participants who have ventilator-associated events in the short and long treatment strategy groups, i.e. $\theta^{\text{MDR}} \neq 0$;

where θ^{MDR} is the treatment effect difference between the proportion of participants in the short and long treatment strategy groups.

e) Total number of days of exposure to antibiotics

Definition: Total duration of antibiotic use during the 60 days of follow-up after enrolment.

H_0 : There is no difference in the total duration of antibiotic use in the short and long treatment strategy groups, i.e. $t^a_s = t^a_l$;

H_1 : There is a difference in the total duration of antibiotic use in the short and long treatment strategy groups, i.e. $t^a_s \neq t^a_l$;

where t^a_s is the duration of antibiotic use in the short and t^a_l is the duration of mechanical ventilation in the long treatment strategy groups.

f) Number and types of extrapulmonary infections during hospitalisation (determined from cultures taken from sterile sites)

Definition: Number and types of bloodstream, bone and joint, intracranial, intraabdominal infections during 60 days of follow-up.

H_0 : There is no difference in the number of sterile site infections in the short and long treatment strategy groups, i.e. $x_s = x_l$;

H_1 : There is a difference in the number of sterile site infections in the short and long treatment strategy groups, i.e. $x_s \neq x_l$;

where x_s is the number of sterile site infections in the short and x_l is the number of sterile site infections in the long treatment strategy groups.

g) Adverse events, i.e. antibiotic related diarrhoea, allergic reactions

Definition: Number and types of adverse events during 60 days of follow-up, which include antibiotic related diarrhoea, allergic reactions, readmissions

H_0 : There is no difference in the number of adverse events in the short and long treatment strategy groups, i.e. $x^{AE}_s = x^{AE}_l$;

H_1 : There is a difference in the number of adverse events in the short and long treatment strategy groups, i.e. $x^{AE}_s \neq x^{AE}_l$;

where x^{AE}_s is the number of adverse events in the short and x^{AE}_l is the number of adverse events in the long treatment strategy groups.

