2.7. Outcomes Assessment Schedule

Baseline assessments are performed prior to randomisation on day 0. Other important assessment time points are detailed below.

Time point (Day)	Activity
0	Enrolment, baseline assessments.
Antibiotic prescription	
0-7	Antibiotic choice(s) is / are checked against respiratory endotracheal tube cultures. If current antibiotic choice(s) is / are not appropriate, primary physicians are advised to switch antibiotic choice according

	
to antibiotic susceptibility report (when there is positive growth) or local microbiology antibiogram (when there is no positive growth).
 
Randomisation to short or long treatment strategy. If randomisation is to short arm, all antibiotics for the participant should be stopped on the day of randomisation (other than, when applicable, anti-tuberculosis antibiotics, prophylaxis e.g. peri or post operative or in immunocompromised hosts, gut prokinetic antibiotics)

0 - discharge	Weekly follow-up for new or changes in antibiotic prescription for all participants.
Outcome assessment	
0 - discharge	
New or changes in antibiotic prescription or new respiratory culture reports will trigger screening for pneumonia recurrence. The US CDC VAP diagnostic criteria will be checked during the preceding week.
 
When these diagnostic criteria are met, two independent respiratory or infectious diseases physicians who are blinded to the randomisation arm will be consulted to verify if the episode is a recurrent episode.

0 - 60	
Mortality is assessed weekly.
 
Secondary outcomes such as adverse events, discharge / readmissions, intubation / extubation, clinical cultures, biochemistry laboratory tests are recorded weekly.

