7.3. Adjustment of P values for Multiple Testing

There is no multiple testing as only a single primary outcome is considered. All additional analyses are undertaken with an intention to further inform the results from the primary analysis. Therefore significance levels used will be 0.05 and 95% confidence intervals will be reported.

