8.2. Ventilator-Associated Events

Episodes of ventilator-associated events will be summarised overall and by treatment arm (frequency and percentages). Participants will be categorised as either having or not having experienced ventilator-associated events. Using this as a binary outcome variable, the analysis described in section 7.2 will be repeated.

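### Ventilator-associated events are defined as the episodes the adjudicators did not verify, so a participant whose only episode is a verified recurrence counts as event-free, and an arm difference can be hidden or reversed

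*SAP*

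**What the plan says.** SAP section 2.6 builds two endpoints from the same CDC VAP criteria. A recurrence, which enters the primary composite, is an episode that meets the criteria and is "verified by two independent respiratory or infectious diseases physicians blinded to the randomisation arm". A ventilator-associated event, the first secondary endpoint, is an event that meets the criteria "but were not verified by two independent respiratory or infectious diseases physicians".

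SAP section 2.7 gives the workflow. A new or changed antibiotic prescription or a new respiratory culture triggers a check of the criteria, and then: "When these diagnostic criteria are met, two independent respiratory or infectious diseases physicians who are blinded to the randomisation arm will be consulted". Their question is whether the episode is a recurrent one. This row of the schedule runs from day 0 to discharge.

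SAP section 8.2 sets the unit of analysis: "Participants will be categorised as either having or not having experienced ventilator-associated events". The section 7.2 analysis is then repeated on that binary outcome. On testing, section 2.6 says: "All statistical tests for the secondary endpoints are standard two-sided superiority tests". Section 7.3 adds that "significance levels used will be 0.05 and 95% confidence intervals will be reported".

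Protocol section 4 lists ventilator-associated events first among the outcomes meant to show other clinical benefits of the shorter course, and does not define them.

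**The concern.** Under this definition a verified recurrence is not a ventilator-associated event. A participant whose only criteria-positive episode was confirmed goes into the event-free group for this endpoint, together with participants who had no episode at all. What is tested is the remainder that the two physicians did not both confirm.

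The endpoint sits under an objective about benefits of the short course, so a lower proportion in the short arm would be read as a benefit. Protocol section 9 itself says that VAP relapse may be more frequent in that arm. If more of the short arm's episodes are confirmed as recurrences, fewer may be left to count here. An excess of criteria-positive episodes could then appear as no difference, or as an advantage.

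**Working it through.** The documents state no event rate, verified share or power for this endpoint, so there is no figure to reproduce. **All rates below are assumptions.** The arm size of 230 comes from SAP section 2.2.

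**1. How the categories fit together**

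| Participant's criteria-positive episodes | Primary endpoint (recurrence) | Ventilator-associated event |
|---|---|---|
| None | No | No |
| Verified only | Yes | No |
| Unverified only | No | Yes |
| Verified and a separate unverified one | Yes | Yes |

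The second row is the problem. The fourth row shows that the exclusion acts on episodes: a verified recurrence does not by itself remove the participant.

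**2. Main illustration**

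Let r be the probability of a verified recurrence, 25% short and 15% long. Let u be the probability of an unverified episode, 20% in each arm.

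- Any criteria-positive episode, 1 − (1 − r)(1 − u): short 1 − 0.75 × 0.80 = 40%; long 1 − 0.85 × 0.80 = 32%. Short is worse by 8 points.
- Endpoint as written, unverified episodes independent of verified ones: u = 20% v 20%. The 8-point difference disappears.
- Endpoint as written, no separate unverified episode in anyone with a verified recurrence, (1 − r)u: short 0.75 × 0.20 = 15%; long 0.85 × 0.20 = 17%. Short looks better by 2 points.

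Precision with 230 per arm:

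- For 15% v 17%, SE = √[(0.15 × 0.85 + 0.17 × 0.83)/230] = 0.034, a 95% half-width of about 6.7 points.
- For 40% v 32%, SE = √[(0.40 × 0.60 + 0.32 × 0.68)/230] = 0.045, a half-width of about 8.7 points.

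Neither difference would be significant at 0.05. The illustration shows a shift in the quantity estimated, not a likely false-positive result.

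**3. When the direction reverses**

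Take at most one criteria-positive episode per participant. Let c be the proportion with such an episode and v the share verified. The endpoint as written is c(1 − v).

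| Criteria-positive, short v long | Verified share, short v long | Verified recurrence, short − long | Endpoint as written, short − long |
|---|---|---|---|
| 40% v 40% | 75% v 50% | 30% − 20% = +10 points | 10% − 20% = −10 points |
| 44% v 40% | 75% v 50% | 33% − 20% = +13 points | 11% − 20% = −9 points |
| 44% v 40% | 60% v 60% | 26.4% − 24% = +2.4 points | 17.6% − 16% = +1.6 points |
| 40% v 30% | 60% v 60% | 24% − 18% = +6 points | 16% − 12% = +4 points |

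In the first row the counts are 69 v 46 verified recurrences (χ² = 6.13, p = 0.013) and 23 v 46 ventilator-associated events (χ² = 9.02, p = 0.003), each out of 230. The number of criteria-positive participants is the same in both arms (92), yet the endpoint as written favours short significantly.

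The break-even verified share in the short arm is 1 − c_long(1 − v_long)/c_short. With c_long = 40% and v_long = 50%, it is 50%, 54.5% and 60% for c_short = 40%, 44% and 50%. Above those shares the endpoint points in favour of short. With equal shares the direction is kept, though the difference shrinks by the factor (1 − v).

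**The case against.** The strongest defence is that a secondary endpoint should not count a primary component again. Verified recurrences are not lost from the report: they enter the primary composite and also appear in the SAE breakdown of SAP section 8.3. That would justify a descriptive row for unverified episodes. It does not justify a superiority test of that remainder under a name that suggests all such events.

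Three stronger readings are tempting, and the documents do not support them:

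- **A reader might infer that unverified means rejected.** The phrase also covers an episode that only one of the two physicians confirmed. Under SAP section 2.4 the experts diagnose persistence as well as recurrence, so an episode judged to be persistence of the index VAP may fall here too. Because the adjudication row in section 2.7 ends at discharge while secondary outcomes are recorded to day 60, some later episodes may not have been reviewed at all. The remainder is mixed.
- **A reader might infer that more recurrences must mean fewer events.** That fails when the verified share is equal in both arms, and when unverified episodes occur independently of verified ones.
- **A reader might take 15% v 17% as the expected result.** It rests wholly on the assumption that participants with a verified recurrence have no separate unverified episode. No section of either document says so.

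The sponsor might also say that the definition was meant to cover episodes irrespective of verification. The contrast drawn in section 2.6 and the workflow in section 2.7 point the other way. If that was the intention, the sentence needs the same correction.

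**Conclusion.** The point holds as a defect in the definition of one tested secondary endpoint. On the text, a participant whose only criteria-positive episode is a verified recurrence is scored as event-free, and neither SAP section 8.2 nor the protocol adds that episode back.

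The consequence is conditional. A difference in criteria-positive episodes can be hidden or reversed when the arms differ in the share verified or when verified recurrences displace unverified episodes. Under the assumed rates, an 8-point disadvantage for short becomes 0 with independence and a 2-point advantage with displacement. A 10-point spurious advantage needs verified shares as far apart as 75% and 50%. The documents do not show which case applies.

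The primary endpoint, the 12% margin, the sample size and the non-inferiority conclusion are unaffected.

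**What to change.** In SAP section 2.6, define the tested endpoint as any post-enrolment episode meeting the CDC criteria, whatever the adjudication result. In section 8.2, report verified and unverified episodes as two descriptive rows by arm, so that a reader can see how the total divides.

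No new data should be needed, because the two existing endpoints already require each criteria-positive episode and its adjudication result.

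The costs are:

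- The endpoint will overlap the recurrence component of the primary endpoint, and the report should say so.
- SAP section 4 requires DSMB approval of an analysis plan amendment.
- SAP section 2.2 shows follow-up ending on 14 February 2023, and section 9.2 says the statistician is not blinded. The amendment should therefore be dated and should state whether it preceded any tabulation of this endpoint by arm.

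If a change to the tested endpoint is no longer acceptable, the minimum is to relabel it as unverified episodes and show the verified and total counts beside it.
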